### 9.3. Dose Adjustments

Dose adjustments (including dose escalation and dose reduction), as reported in the dose exposure CRF page, will be summarized by treatment arm and include the following:

- Any dose adjustments;
- Dose adjustment due to AE;
- Dose adjustment due to AML relapse/progression;
- One dose reduction;
- Two dose reductions;
- Dose escalation (to 300mg × 21 days).

Dose adjustment is defined as subjects who have reported at least one dose adjustment in the dosing CRF page. One dose reduction is defined as subjects have reduced assigned dose from 300mg × 14 days to 200mg × 14 days. Two dose reduction is defined as subjects have reduced assigned dose from 300mg × 14 days to 200mg × 14 days, and then from 200mg × 14 days to 200mg × 7 days. Dose escalation is defined as subjects who have received at least one assigned dose of 300mg × 21 days.

In addition, time to first dose adjustment due to AE, time to first dose adjustment due to AML relapse/progression, reason for first dose adjustment and reason for first dose escalation will also be summarized.

### 9.4. Treatment Compliance

As part of the routine recording of the amount of IP taken by each subject, the dose start and end dates, dose assigned and actual dose administered will be recorded in the CRF. These records will be used to calculate compliance.

The compliance rate (%) for each subject will be computed as 100 times the cumulative dose (in mg) taken over the period divided by the intended cumulative dose (in mg) that should have been taken over the same period. It will be calculated for each subject for each cycle of treatment and overall.

Overall compliance will be summarized using descriptive statistics overall and by cycle. Additionally, the number and percentage of subjects will be summarized by category < 75%, ≥75 to ≤ 120%, and > 120%.

## 11. EFFICACY ANALYSIS

All efficacy evaluations will be conducted using the ITT population. Supportive analysis of the primary and key secondary efficacy endpoints using the mITT population will be conducted. Statistical comparisons will be made between oral azacitidine and placebo.

### 11.1. General Statistical Methods

All hypothesis testing will be carried out at the 5% (2-sided) significance level and designed to evaluate the superiority of oral azacitidine relative to Placebo.

The study randomization scheme was stratified according to 4 prognostic features: age at time of induction therapy 55-64 versus  $\geq 65$  years; prior history of MDS: yes versus no; cytogenetic risk status at time of induction therapy: intermediate risk versus poor risk; and received consolidation therapy following induction therapy: yes versus no, resulting in 16 strata. The statistical analyses conducted to compare treatment arms will include methods that are stratified according to the randomization scheme, using the stratification factors as collected in the clinical database (for subject with missing stratification factor, the missing stratification factor value will be imputed by the data entered via the IVRS). Additionally, for primary endpoint OS and key secondary endpoint RFS, the stratified analysis using IVRS data may also be conducted. It is possible that the number of subjects in an individual stratum may be very small. In order to facilitate inferential statistical analysis, if the minimum number of subjects in a stratum is less than 16 (irrespective of treatment arm), then only the 3 stratification variables that result in the largest minimum stratum size will be used for analysis purposes. Analyses will not be stratified by investigative center, as the recruitment for many centers is likely to be very small.

The general procedure for the analysis of the time-to-event efficacy variables will be as follows. Time-to-event variables will be measured in days but presented in months on tables and figures. A Kaplan-Meier (KM) survival analysis will be performed (unadjusted for the stratification variables). The resulting survival estimates will be presented graphically for selected endpoints. The median, 25th and 75th percentile time-to-event data will be presented with 95% confidence intervals (CIs) (if they can be estimated). The numerical difference (and CI of the difference) in the median, 25th and 75th percentiles between oral azacitidine and placebo will be presented for the unstratified analysis. Differences will be calculated as oral azacitidine - placebo. The 95% CI for the difference will be derived using Kosorok's method ( ). One-year and two-year survival rates with 95% CIs and the difference in survival rates between oral azacitidine and placebo with 95% CI for the difference will also be presented for OS. The CI for the difference between treatment arms in the 1-year proportions will be calculated using Greenwood's variance estimate ( ).

For the primary efficacy analysis of OS, oral azacitidine will be compared to placebo using the stratified log-rank test to assess superiority. The null hypothesis is that the survival curves are equivalent. The stratified Cox proportional hazard regression model will be used to estimate the hazard ratio (HR) and associated 95% CIs for the HR.

The censoring distributions of the treatment arms will be assessed using KM methods. Reverse KM estimates for OS will be calculated to assess the censoring distributions, where observations

in the original analysis that were events (i.e., deaths) will be censored and observations that were censored will be treated as events. The median, 25th and 75th percentiles will be presented and KM curves will be displayed graphically by treatment arm. Additionally, reasons for censoring (e.g., lost to follow-up, withdrew consent, alive at data cut-off) will be summarized (n, percent) for the OS endpoint. The median of the reverse OS KM distribution will be used as the estimate of the median follow-up time [REDACTED]

In order to accommodate tied time-to-event data, the EXACT option within SAS PROC PHREG will be used. This method assumes that there is a true but unknown ordering for the tied event times, and that the ties are merely the results of imprecise measurements of time.

For the categorical efficacy variables, comparison of treatment arms will be via Fisher's exact test, ignoring strata.

A sequential gate-keeping approach will be used to control the overall type I error rate in order to perform hypothesis testing on multiple endpoints. Two endpoints, the primary efficacy endpoint of OS and the key secondary endpoint of RFS, will be tested sequentially in the pre-specified order. The primary efficacy endpoint will be tested first at the two-sided 0.05 significant level. In order to preserve the overall alpha level at 0.05 across the OS and RFS endpoints, formal statistical inference for the RFS analyses can only be made if superiority of oral azacitidine is demonstrated for the primary efficacy endpoint OS, at the two-sided 0.05 significance level.

Other than the pre-specified sequential testing of OS and RFS, no additional alpha adjustments for multiplicity will be made.

## **11.2. Analysis of Primary Efficacy Endpoint**

The primary efficacy variable, time from randomization to death from any cause will be defined as the number of days from the date of randomization until the date of death from any cause, and is calculated by the formula: date of death - date of randomization + 1. Subjects surviving at the end of the follow-up period, or who withdraw consent, or who are lost to follow up will be censored at the date last known alive. For subjects who have withdrawn consent during the study, the last date known alive will be the date of consent withdrawal from the study. For all other subjects, the last date known alive will be derived by searching through all valid assessment dates in all study datasets to identify the last valid subject assessment date available for each subject.

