### 11.2.2. Sensitivity Analysis

The primary efficacy analysis, as described above, will be repeated using the mITT population as a sensitivity analysis.

To assess the potentially confounding effects of other therapy received subsequent to the study treatment, the following additional sensitivity analysis will be performed.

1. Censoring for the use of any subsequent therapy (including post-treatment transplant) for AML. For this analysis, subjects who received any subsequent therapy for AML following discontinuation from their study drug will be censored on the earlier of first subsequent therapy date, or transplant date, regardless of their survival status at the time of the final analysis.
2. Censoring for the use of disease modifying subsequent AML therapy, which is defined as any subsequent AML therapy that is not hydroxycarbamide.
3. Censoring for post-treatment transplant. For this analysis, subjects who received post-treatment transplant will be censored at the time of the transplant.

These modified time to death endpoints will be based on the ITT population and analyzed using the same methods described previously for the primary efficacy endpoint. In addition, based on the 13 April 2018 Type C Guidance meeting with the Agency on the analysis issues with subsequent therapy, the following analyses will be performed to further investigate impacts of subsequent AML therapy on the overall survival. The following methods are planned:

- Cox proportional hazard model with covariates adjustment will include, but not limited to, subsequent AML therapy (time-varying (yes or no)); treatment-by-subsequent AML therapy interaction; baseline characteristics such as age, ECOG score, cytogenetic risk status, CR/CRi status at randomization, etc. The covariates included in the final Cox model will be selected using stepwise variable selection procedure.
- Inverse probability of censoring weighted (IPCW) method. The IPCW modeling approach was introduced by Robins et al and estimates hazard ratios that are valid in the

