#### 11.3.1. Key Secondary Endpoint – Relapse-free Survival (RFS)

##### Primary analysis

Relapse-free survival is defined as the time from the date of randomization to the date of documented relapse or death from any cause, whichever occurs first. Subjects who are still alive without documented relapse, or who were lost to follow-up or withdrew consent without documented relapse, will be censored at the date of their last bone marrow assessment. Relapse is defined according to the IWG AML response criteria. See Appendix 17.7 for definitions of response categories. Documented relapse is defined as, the earliest date of the following

- $\geq 5\%$  bone marrow blasts (myeloblasts) from Central Pathology report, or
- appearance of  $> 0\%$  blasts in the peripheral blood with a later bone marrow confirmation (bone marrow blast [myeloblasts]  $\geq 5\%$ ) within 100 days, or
- at least 2 peripheral blasts  $\geq 5\%$  within 30 days.

Peripheral blasts reported from both Central Pathology and Central lab will be considered. Subjects who withdrew for any reason or received another therapy for AML without documented relapse will be censored on the date of their last bone marrow assessment, prior to receiving any other therapy for AML. Subjects who are still on treatment at the time of study closure without documented relapse will be censored on the date of their last bone marrow assessment. These rules are based on FDA guidance for cancer trial endpoints [REDACTED], and table 2 specifies the application of the guidance for various common situations for the calculation of RFS.

**Table 2** Primary Censoring Rules for RFS

Situation	Derivation Rules	Situation Outcome

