### **Time to discontinuation from treatment**

Time to discontinuation from treatment will be assessed and is defined as the interval from the date of randomization to the date of discontinuation from IP. Subjects who are ongoing in treatment at the time of study closure will be censored at the date of last visit.

Time to discontinuation from treatment will be analyzed using a competing risk model with reason for treatment discontinuation classified as:

- Disease relapse
- Adverse event(s)
- Became eligible for bone marrow or stem cell transplant
- Withdrawal of consent / lost to follow-up / protocol violation /Other
- Death

Cumulative incidence curves will be estimated and summarized for each specific reason for discontinuation from treatment by treatment arm.

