## **14. INTERIM ANALYSIS**

### **14.1. General Information**

One interim analysis to assess futility was planned-in the protocol-when approximately 30% of the total events (99 deaths) have occurred. A beta-spending function was used to calculate a futility boundary of  $Z < -1.9796$  using Gamma(-10) and corresponds to a conditional power level of approximately 18%. The interim analysis was performed with a data cutoff date of 31Dec2015, when 104 deaths occurred. The DMC meeting was held on 23 Mar 2016 where DMC members reviewed unblinded efficacy and safety data. The DMC concluded that the hazard ratio of the CC-486 over placebo remained within the protocol pre-specified futility boundary, and the AE profile did not raise any unexpected safety concerns. Therefore, the DMC recommended that the study could continue as planned.

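### Does the lack of a stated data cut-off in the SAP's overall survival rule leave the primary test open?

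*SAP*

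**What the plan says.** SAP 11.2 defines OS from randomization to death. For those without a death date, "Subjects surviving at the end of the follow-up period, or who withdraw consent, or who are lost to follow up will be censored", using the last day each was known to be alive. Apart from consent withdrawals, that date is "derived by searching through all valid assessment dates in all study datasets to identify the last valid subject assessment date available for each subject". No calendar limit is attached.

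Other parts of the SAP name the end of the data differently:

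- 11.1: "reasons for censoring (e.g., lost to follow-up, withdrew consent, alive at data cut-off) will be summarized" for OS, so a cut-off is taken for granted.
- 11.2.2: subjects are censored at subsequent therapy "regardless of their survival status at the time of the final analysis".
- 11.3.1: "Subjects who are still on treatment at the time of study closure without documented relapse will be censored" at the last marrow assessment.
- 11.3.2: "Subjects who are ongoing in treatment at the time of study closure will be censored at the date of last visit".

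For the interim, SAP 14.1 is explicit: 99 deaths were planned, and "The interim analysis was performed with a data cutoff date of 31Dec2015, when 104 deaths occurred".

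The protocol supplies the trigger. Sections 4.1 and 4.3 close the study at 330 deaths. Section 10.6.1 censors subjects alive at study termination at their last contact. SAP 4.1.3 runs survival follow-up to the end of the study.

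**The concern.** Consider a subject who is alive when the 330th death occurs and who dies before database lock. Under the censoring reasons in SAP 11.1 this subject is alive at the cut-off. Under the literal wording of 11.2, the death is in the database and is an event. Two programmers could thus feed different death counts into the stratified log-rank test. That test is the only confirmatory test of OS, and it opens the gate to RFS.

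The contrast with the interim sharpens the point. There the SAP reports a planned count, a dated cut-off and the actual count. For the final analysis the visible text gives only the 330 deaths of the sample-size section. If the choice were made with knowledge of the results, the primary p-value could be steered.

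**Working it through.** **Inputs (SAP 4.4, Protocol 10.3).** Median OS 16 and 22.9 months; 230 subjects per arm; 5% drop-out over 60 months; accrual over 36 months at 25%, 25% and 50% per year; one-sided alpha 0.025; power 90% at a hazard ratio (HR) of 0.70. Not given: the interval from final cut-off to lock. I assume 1 to 6 months.

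**Step 1: the plan's own figure.** Schoenfeld events = 4(1.960 + 1.282)² / (ln 0.70)² = 330.4, against 330 stated. The figure reproduces.

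**Step 2: the death rate after the trigger.** Monthly hazards are λ = ln 2/16 = 0.0433 and ln 2/22.9 = 0.0303; drop-out is η = −ln(0.95)/60 = 0.00085. Expected deaths by month t are the sum over arms of 230 × the average over entry times e of [λ/(λ+η)] × [1 − exp(−(λ+η)(t−e))]. This gives the 99th death at month 27.6 (the plan says about 28) and the 330th at month 58.9 (the plan says 60), so the model follows the plan. Expected deaths after the 330th:

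| Gap to lock | Design hazards | Hazards scaled so the 330th death falls at month 91 |
|---|---|---|
| 1 month | 4.2 | 2.4 |
| 2.73 months (83 days) | 11.2 | 6.5 |
| 3 months | 12.3 | 7.1 |
| 6 months | 23.2 | 13.7 |

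The last column uses uniform accrual over the 53 months in Protocol 4.3, with both hazards multiplied by 0.59. The 83 days is the interval between the interim cut-off and the DMC review ("The DMC meeting was held on 23 Mar 2016 where DMC members reviewed unblinded efficacy and safety data"). It is only a reference point, since a DMC meeting is not a database lock. Accrual shape hardly matters: uniform 53-month accrual with the design hazards also gives 12.3 deaths in 3 months. The gap and the hazard do matter.

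**Step 3: the effect on the test.** With D deaths, the largest significant HR is exp(−2 × 1.96/√D), and power at HR 0.70 is Φ(0.3567 × √D/2 − 1.96). The chance that the test at 330 deaths and the test at D deaths give different verdicts comes from a bivariate normal with means −ln(HR) × √330/2 and −ln(HR) × √D/2 and correlation √(330/D), each compared with 1.96.

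| Deaths | Largest significant HR | Power at HR 0.70 | Verdicts differ, HR 0.70 | HR 0.80 | HR 1 |
|---|---|---|---|---|---|
| 330 | 0.806 | 90.0% | – | – | – |
| 332 | 0.806 | 90.1% | 1.1% | 2.5% | 0.4% |
| 334 | 0.807 | 90.3% | 1.5% | 3.5% | 0.5% |
| 341 | 0.809 | 90.9% | 2.6% | 5.8% | 0.8% |
| 353 | 0.812 | 91.8% | 3.7% | 8.5% | 1.2% |

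The last three columns are not error rates. They say how often two valid tests on overlapping data fall on opposite sides of the line, in either direction. The net difference is the power column. A log-rank simulation (8,000 trials per scenario, uniform 53-month accrual, cap at the 330th death against 83 days later) agrees. Power at HR 0.70 was 89.5% and 90.6%, and one-sided error at HR 1 was 2.3% under both rules.

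**Step 4: can the choice be steered?** SAP 4.3 keeps subjects, investigators, site staff and the sponsor's clinical and medical personnel blinded until lock. A cut-off set before then cannot depend on results by arm. Extension Phase deaths cannot slip in either: that phase starts after unblinding (SAP 4.1.4), and blinding ends at lock.

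**The case for a change.** The strongest case for a change is that the protocol's own terms for the end of the study are not uniform. The Protocol Summary defines the end of the trial by the last visit or the last required data point, whichever is later. Extension Phase follow-up also runs until study closure, which there must come after the 330-death trigger. So *study closure*, which the SAP uses for RFS and time to discontinuation, has two possible meanings. Neither document says what to do with deaths between the 330th and lock. The extraction date in SAP 5.1 is a reporting convention, not a clinical cut-off. A few sentences would settle all this at no cost.

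The textual part stands: SAP 11.2 does not carry the 330-death trigger into its rule, and one term throughout would read better. Three things limit it. First, the trigger is not missing. Protocol 4.1 and 4.3 tie closure to 330 deaths, and Protocol 10.6.1 ties OS censoring to study termination. Second, a cut-off can be applied when the datasets are extracted; a search through all study datasets is then already bounded. Third, SAP Section 2 is redacted and Sections 10, 13 and 16 are not visible, so a dated rule may exist there.

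**Conclusion.** This is a gap that analysts fill sensibly. The plan presupposes a cut-off for OS, the protocol says what triggers it, and the interim shows that the sponsor works with dated cut-offs. Writing the date down would be tidy, but it would not make the result sounder, because counting or excluding the late deaths is valid either way.

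The size is small: about 2 to 23 deaths on top of 330, at most 0.006 on the critical hazard ratio and at most 1.8 percentage points of power, always upwards. The two readings would give different verdicts in about 1% to 4% of trials at the design hazard ratio, and in up to about 8.5% at 0.80.

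The conclusion rests on exponential survival, a gap to lock of 1 to 6 months (an assumption, since no document gives it), and a cut-off fixed before unblinding. If the date were chosen with knowledge of results by arm, the conclusion would fail; nothing in the visible text points that way.

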### **11.2.1. Primary Efficacy Analysis**

The primary efficacy analysis will be performed using the ITT population. The null hypothesis for testing the primary efficacy endpoint, time to death from any cause, is that the overall survival distributions for the oral azacitidine and placebo groups are equivalent. The analysis of the primary efficacy endpoint will be conducted using a stratified log-rank test, stratifying by age at time of induction therapy, prior history of MDS, cytogenetic risk category, received consolidation therapy following induction therapy. The p-value from the stratified log-rank test will be the p-value for primary analysis. The p-value from unstratified log-rank test will also be

provided. The KM method will be used to estimate the survival distribution functions for each treatment arm. KM estimates for median OS as well as the 25th and 75th percentiles and associated two-sided 95% CIs will be summarized for each treatment arm. In addition, the numerical difference, and 95% CI of the difference, in the median, 25th, and 75th percentiles between the two treatment arms will be presented. Plots of the KM survival curves will be presented for the two treatment arms, unadjusted for the stratification variables. A stratified Cox proportional hazards model will be used to estimate the hazard rate ratio and the corresponding 95% CI for oral azacitidine relative to placebo.

Additionally, KM methods will be used to estimate the 1-year and 2-year survival probabilities for time to death from any cause. Estimates of the 1-year (365 days) and 2-year (730 days) survival probabilities and corresponding 95% confidence intervals will be presented by treatment arm. Kaplan Meier methods will also be used to estimate the death probabilities at 30, 90 days, 6 months and 1 year. The death rate (count and percent) at 30, 90 days, 6 months and 1 year will also be summarized.

### 11.2.2. Sensitivity Analysis

The primary efficacy analysis, as described above, will be repeated using the mITT population as a sensitivity analysis.

To assess the potentially confounding effects of other therapy received subsequent to the study treatment, the following additional sensitivity analysis will be performed.

1. Censoring for the use of any subsequent therapy (including post-treatment transplant) for AML. For this analysis, subjects who received any subsequent therapy for AML following discontinuation from their study drug will be censored on the earlier of first subsequent therapy date, or transplant date, regardless of their survival status at the time of the final analysis.
2. Censoring for the use of disease modifying subsequent AML therapy, which is defined as any subsequent AML therapy that is not hydroxycarbamide.
3. Censoring for post-treatment transplant. For this analysis, subjects who received post-treatment transplant will be censored at the time of the transplant.

These modified time to death endpoints will be based on the ITT population and analyzed using the same methods described previously for the primary efficacy endpoint. In addition, based on the 13 April 2018 Type C Guidance meeting with the Agency on the analysis issues with subsequent therapy, the following analyses will be performed to further investigate impacts of subsequent AML therapy on the overall survival. The following methods are planned:

- Cox proportional hazard model with covariates adjustment will include, but not limited to, subsequent AML therapy (time-varying (yes or no)); treatment-by-subsequent AML therapy interaction; baseline characteristics such as age, ECOG score, cytogenetic risk status, CR/CRi status at randomization, etc. The covariates included in the final Cox model will be selected using stepwise variable selection procedure.
- Inverse probability of censoring weighted (IPCW) method. The IPCW modeling approach was introduced by Robins et al and estimates hazard ratios that are valid in the

presence of informative censoring at start of subsequent therapy. The method adjusts for subsequent therapy by recreating the population that would have been evaluated in the absence of any subsequent therapy by weighting the follow-up for those subjects who did not receive additional therapy in order to account for the follow-up of subjects who did receive subsequent therapy that has been (informatively) censored. The weights are determined by matching demographic and baseline characteristics as well as post randomization clinical factors for subjects who did and did not receive subsequent therapy. Baseline covariates include the following: age, sex, ECOG score, cytogenetic risk status at diagnosis, prior history of MDS, geographic region, CR/CRi first achieved after induction, time to first achieving CR/CRi, CR/CRi status at randomization, MRD status at randomization, with or without consolidation, # of consolidation cycles received, platelet and ANC counts. Post randomization factors include platelet count, ANC, binary indicator of history of grade 3 or 4 AE, binary indicator of occurrence of a grade 3 or 4 since last visit, time since last visit (months), bone marrow blast %, and ECOG score. Each subject is weighted equal to the inverse probability of not receiving additional treatment. Adjusted HRs for the treatment effect are then estimated from Cox regression models with adjustment for subsequent therapy (i.e., censoring at time of subsequent therapy), both with and without further adjustment for baseline covariates.

- Regression based imputation analysis method proposed by Luo, X. et al that allows for inferences about the treatment effect in the presence of confounding due to additional therapy received subsequent to the study treatment. This method provides adjusted estimates of the KM survival curves, which allows for comparisons using the log-rank test and the calculation of an adjusted HR and associated confidence intervals.

At the final analysis, the assumption of proportional hazards will be tested by a time-dependent Cox model with interaction of treatment and time. A figure of hazard function over time will give an instinct idea of hazard trend over time.

If proportional hazard assumption is violated, the following sensitivity analyses will be conducted using ITT population:

1. Restricted mean survival time will be generated and compared between oral azacitidine and placebo arms;
2. Piecewise cox regression will provide hazard estimates at the following intervals,  $\leq 3$  months,  $3 < \leq 6$  months,  $6 < \leq 12$  months and  $> 12$  months;
3. In the presence of non-proportional and early OS separation, a generalized Wilcoxon test will be utilized to compare survival curves.

To evaluate the impact of censoring in the primary analysis due to subjects who withdrew consent from survival follow-up, a sensitivity analysis of the OS endpoint will be performed. For this analysis, subjects who withdrew consent from survival follow-up will be treated as an event rather than as a censored observation. This sensitivity analysis will be based on the ITT population.

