### **4.3. Stratification, Randomization, and Blinding**

Randomization will be carried out using an Interactive Voice Response System (IVRS). Treatment assignment will follow a 1:1 ratio between two treatment arms. Randomization method was based on permuted-block randomization. Randomization was stratified by the following factors: age at time of induction therapy (55-64 versus  $\geq 65$  years); prior history of MDS (yes versus no); cytogenetic risk category at time of induction therapy (intermediate risk versus poor risk); received consolidation therapy following induction therapy (yes versus no).

This is a double-blind study. Subjects, investigators, site staff and Celgene Corporation clinical and medical personnel will be blinded of treatment assignments until database lock.

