### **4.4. Sample Size Determination**

The equality of OS curves will be compared between the oral azacitidine and placebo treatment arms using a stratified log-rank test. Assuming a median OS of 16 months in the placebo treated group ([REDACTED]), a median OS of 22.9 months in the oral azacitidine treated group (43% improvement), and a study duration of 60 months with a drop-out rate of 5% from both treatment arms, over the duration of the study, this design requires 330 deaths and approximately 460 subjects (230 per treatment arm) to be randomized in order to achieve at least 90% power to detect a constant hazard ratio of 0.70 and demonstrate a statistically significant difference in OS. It is assumed that the OS distribution is exponential with a constant failure (hazard) rate and that accrual is non-uniform during an accrual period of 36 months with 25% of the subjects accrued during each of the first 2 years of enrollment (50% accrued at 24 months) and the remaining 50%

accrued during the last year of enrollment. Sample size calculations are based on a one-sided alpha of 0.025 with one interim analysis for futility after 30% of the events have occurred.

Sample size was calculated using the East® Version 5.4 software system [REDACTED] [REDACTED]).

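### Stepwise selection in the supportive Cox model for subsequent therapy lets the data decide what its treatment hazard ratio means

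*SAP*

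**What the plan says.** SAP 11.2.2 lists several methods, introduced with reference to an agency meeting, for looking into how later AML therapy affects overall survival. The first opens: "Cox proportional hazard model with covariates adjustment will include, but not limited to, subsequent AML therapy (time-varying (yes or no"). It goes on to name the treatment-by-therapy interaction and some baseline characteristics (age, ECOG score, cytogenetic risk, CR/CRi status at randomization), and it leaves that list open at the end as well as at the start. The bullet closes: "The covariates included in the final Cox model will be selected using stepwise variable selection procedure".

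The section gives no entry or stay threshold, no forced terms, and no statement of which coefficient or contrast is to be reported as the treatment effect.

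Two neighbouring passages matter:

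- SAP 11.2.1 takes the primary result from the stratified log-rank test, with a stratified Cox hazard ratio, in the ITT population.
- The IPCW bullet in SAP 11.2.2 names its baseline covariates, including prior MDS, consolidation and MRD status. It also names time-updated factors, including marrow blast percentage and ECOG score.

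**The concern.** The interaction is one of the covariates listed just before the selection rule, so on its plain wording the rule applies to it. The interaction fixes the meaning of the treatment coefficient. A rule that keeps or drops it on the strength of the data therefore chooses the quantity reported, as well as how precisely it is estimated.

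The therapy term has its own problem. Disease relapse is a listed reason for stopping study drug (protocol section 12), and SAP 11.2.2 defines subsequent therapy as treatment received after stopping. Patients who start it have often just relapsed and face a higher death hazard. The covariates the SAP names for this model are all baseline, so the therapy coefficient absorbs that excess hazard.

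At stake is how a reader answers the question behind these analyses: whether later therapy explains the survival result. No alpha depends on the model.

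**Working it through.** **1. The plan's own figure.** The documents give no figure for this model, so the check starts from the design in SAP 4.4: "Sample size calculations are based on a one-sided alpha of 0.025", with "90% power to detect a constant hazard ratio of 0.70" and 1:1 allocation. Schoenfeld's formula gives

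deaths = 4(1.960 + 1.282)² / (ln 0.70)² = 330.4, rounded up to 331.

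The SAP states 330. Power at 330 deaths is Φ(½√330 × 0.3567 − 1.960) = 0.8997. The design figure reproduces and is not in dispute.

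**2. What each model estimates.** Let A be treatment, S(t) subsequent therapy started by time t, and Z the baseline covariates:

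h(t) = h₀(t) exp{β₁A + β₂S(t) + β₃A·S(t) + γ′Z}.

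- Interaction kept: exp(β₁) is the treatment hazard ratio before therapy, and exp(β₁ + β₃) is the one after it.
- Interaction dropped: exp(β₁) is a single hazard ratio conditional on S(t), which treatment can affect.
- Neither is the overall hazard ratio.

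**3. Assumptions for the simulation.** From SAP 4.4: 460 subjects, the stated accrual pattern over 36 months, and 60 months in all. The following are assumed, because the documents do not give them:

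- placebo relapse rate 0.12 per month;
- death rate 0.008 per month before relapse and 0.10 after it;
- 70% of relapsers receive therapy, which multiplies the death hazard by 0.7;
- azacitidine acts on relapse only (hazard ratio 0.50);
- eight baseline covariates, four of them prognostic.

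**4. Large sample (200,000 subjects), no selection.**

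| Quantity | Hazard ratio |
|---|---|
| Overall (ITT) | 0.72 |
| Treatment before therapy, interaction in | 0.617 |
| Treatment after therapy, 0.617 × 1.566 | 0.97 |
| Treatment, interaction out | 0.80 |
| Therapy on placebo (true value 0.7) | 1.78 |
| Therapy on azacitidine, 1.777 × 1.566 (true value 0.7) | 2.78 |

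With no treatment effect (and no baseline covariates), every treatment hazard ratio was about 1.01. The models part company only when there is an effect.

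**5. Stepwise selection at 460 subjects, treatment forced in.**

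| Setting | Overall HR | Interaction kept: runs, mean treatment HR | Interaction dropped: runs, mean treatment HR |
|---|---|---|---|
| Entry and stay p = 0.05 | 0.72 | 103/200, 0.56 | 97/200, 0.80 |
| Entry and stay p = 0.15 | 0.71 | 149/200, 0.58 | 51/200, 0.77 |
| Separate check, other assumed rates | 0.71 | 59/150, 0.62 | 91/150, 0.80 |

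How often the interaction survives also depends on the threshold, which the SAP does not give.

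**6. The therapy coefficient.** In a separate simulation, therapy truly halved the death hazard after relapse and azacitidine acted on relapse only (hazard ratio 0.6). Over 12 settings the fitted therapy hazard ratio was 0.85 to 3.30 on placebo and 1.16 to 4.31 on azacitidine. It exceeded 1 in 22 of 24 estimates and was never near 0.5. Other assumed rates with the same true value gave 1.3, about 2.2 and 2.6. The upward bias persists; its size moves with the assumed rates.

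**The case against.** **The bullet can be read as fixing the key terms.** It says the model will contain therapy and the interaction, so perhaps only baseline factors are selected. Under that reading a simulation found almost no cost. The treatment hazard ratio with stepwise against a fixed list was 0.706 v 0.704 in one setting and 0.673 v 0.671 in another. Mean standard errors were 0.138 v 0.139 and 0.125 v 0.126, and the false-positive rate was 4.0% for both. This stands for that reading. However, the closing sentence applies selection to the covariates without exempting any, and even on this reading the reported contrast is undefined and the therapy coefficient is confounded.

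**The model is never said to measure the overall effect.** Correct. Its stated purpose is to explore the impact of later therapy. The fault is an unfixed model with no declared contrast, not a false statement.

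**Relapse is not excluded, because the list is open.** Also correct: relapse could be added. But nothing commits the analyst to adding it, and every adjustment actually named is baseline.

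**The IPCW analysis already deals with changing disease status.** It does, through time-updated blasts, counts and ECOG score, and censoring and imputation analyses are planned too. This limits the harm and supplies the better source for a therapy-adjusted effect. It does not specify the Cox model.

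**The agency's advice cannot be seen.** True, so nothing here rests on what it did or did not recommend.

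**Conclusion.** The point holds as a cheap improvement to a supportive analysis. On its plain wording, SAP 11.2.2 lets the data choose between two treatment hazard ratios with different meanings: about 0.56 to 0.62 against 0.77 to 0.80 in the simulations, where the overall value was about 0.71 to 0.72. The therapy coefficient is biased towards harm by relapse. The sizes rest on assumed relapse, death and therapy rates and should not be read as forecasts for this trial.

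A reader might infer three stronger things that the documents do not support:

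- **That the overall survival result is in doubt.** The log-rank test and stratified Cox hazard ratio of SAP 11.2.1 do not use this model.
- **That the treatment confidence interval must be too narrow.** This did not appear when treatment, therapy and interaction were forced in.
- **That treatment itself may be selected out.** In simulation this happened in 39% of runs at p = 0.05 when treatment was not forced in. The SAP does not say treatment is open to selection; it only omits to say that it is forced.

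**What to change.** Before unblinding, amend the Cox bullet in SAP 11.2.2 to:

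1. Drop stepwise selection.
2. Force in treatment, time-varying therapy and their interaction.
3. Close the baseline list: the four stratification factors, ECOG score, and CR/CRi and MRD status at randomization. Prior MDS and consolidation are stratification factors the bullet does not now name, though the IPCW bullet names both.
4. Report the treatment hazard ratios before and after therapy as descriptive. State that neither is the overall effect and that the therapy coefficient is not causal.
5. Take the therapy-adjusted effect from the planned IPCW analysis, subject to its own assumptions.

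The cost is SAP wording only, with no new data. The downside is that a fixed list may carry a few weak covariates.
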